6.15 Study Procedure Flow Chart

7 Safety and Effectiveness Assessments

7.1 Safety Assessments

Subjects will be observed for several hours after GAE to monitor for immediate complications to include bleeding, infection and acute ischemia of the lower extremity. The subjects will be given a phone number that they can call to reach the principal investigator or designee if they believe they have developed a complication of the procedure. If at any point during the study period (including between scheduled follow-up visits) a subject reports symptoms that suggest an AE, an appropriate work-up will be initiated by the investigators to evaluate the etiology of the symptoms. This may include physical exam, laboratory tests and imaging (including MRI if appropriate).

7.2 Effectiveness Assessments

Technical success will be defined as devascularization of hypervascular synovium at the affected knee. This will be determined during the procedure. Clinical success will be defined as a 16% reduction of the baseline global WOMAC score at 1 or 6 month follow-up (primary outcome) and a 15% reduction of the baseline pain VAS score at 6 or 1 month follow-up (primary outcome).

8 Statistical Plan

8.1 Sample Size Determination

Using baseline WOMAC means and standard deviations of 12.2 and 1.9, respectively, from the Okuno study, we will have at least 69.1 % power to detect a clinically relevant difference of 16% for WOMAC for a one-sided alternative hypothesis. Actual power will be greater than this 69.1% lower bound since our analysis strategy uses data from multiple time points to formulate individual growth trajectories.

Using baseline VAS means and ranges of 72 and (54-100), respectively, we used the method of devised by S.P. Hozo, B. Djulbegovic, and I. Hozo to derive an estimate of the baseline standard deviation as 13.3. Given these parameters, we will have at least 51.7 % power to detect a clinically relevant difference of 15% for VAS for a one-sided alternative hypothesis. Actual power will be greater than this 51.7% lower bound since our analysis strategy uses data from multiple time points to formulate individual growth trajectories.

Power calculations used GPower, version 3.1.9.2.

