3.2 Primary Study Endpoints

1. Overall efficacy of treatment as determined by a minimal clinically significant reduction in global Western Ontario and McMaster University

Osteoarthritis Index (WOMAC) questionnaire scoring of 16% at 1 and 6 month follow-up.

2. Minimal clinically important decrease of 15% on the pain VAS at 1 or 6 months follow-up.

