8.2 Statistical Methods

The primary study endpoints, WOMAC and VAS scores, will be collected at baseline, 1 month follow-up, 3 month follow-up, and 6 month follow-up. Mean WOMAC and VAS scores will be reported at baseline, 1 month follow-up, 3 month follow-up, and 6 month follow-up, along with associated confidence intervals.

We will address the primary study endpoints by modeling each clinical outcome using random coefficient modeling. The clinical outcomes will be modeled as a linear function of time. We will allow a random intercept and slope that is dependent on treatment, so that each patient will have their own trajectory of pain over time. No additional covariates will be included in the model. We will employ a compound symmetric R-side covariance structure to account for dependencies arising from observations from the same patient. Random coefficient models are robust to missing values only require data to be MAR (and not the stronger assumption of MCAR), so that presence of missing values will not invalidate our conclusions.

We will compute predicted means, as well as the estimated difference in predicted means, at 6 months for both WOMAC and VAS; these will be derived from the population-averaged trajectories (i.e. fixed effects). We will test the H₀: $\mu_{sham, 6}$ months - $\mu_{GAE, 6 \text{ months}} = 0$ versus the one-sided alternative hypothesis H_a: $\mu_{sham, 6}$ months - $\mu_{GAE, 6 \text{ months}} > 0$ using a Wald test. Both primary study endpoints will be evaluated by considering significance of the p-value (p < 0.05) along with the percentage predicted mean difference with respect to the clinically relevant differences (16% for WOMAC and 15% for VAS). Both these factors will be taken in tandem as evidence to suggest GAE treatment efficacy. Primary endpoints will be assessed only at one time point, so that adjustment for multiple comparisons is not necessary since the evaluation of the primary endpoints for WOMAC and VAS each consists of only one statistical test. Non-significance of the p-value for this test will be considered inconclusive evidence against the null hypothesis. Variance components, including the intraclass correlation coefficient, will also be reported for each model. All analyses will use SAS version 9.4 (SAS Institute, Inc., Cary, NC).

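### The powers in 8.1 cover the significance test alone; for the two-part efficacy criterion in 8.2, read naturally, the chance at the design effect is about 50% (WOMAC) and 47% (VAS)

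*Combined protocol and SAP*

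**What the plan says.** Section 8.1 takes a baseline WOMAC mean of 12.2 (SD 1.9) and a baseline VAS mean of 72 (SD 13.3, estimated from the range). It reports at least 69.1% power for a 16% WOMAC difference and at least 51.7% for a 15% VAS difference, both one-sided. For WOMAC it adds "Actual power will be greater than this 69.1% lower bound since our analysis strategy uses data from multiple time points", and it makes the same statement for VAS.

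Section 8.2 compares the predicted sham and GAE means at 6 months with a one-sided Wald test. Each endpoint is judged by p < 0.05 "along with the percentage predicted mean difference with respect to the clinically relevant differences (16% for WOMAC and 15% for VAS"), followed by "Both these factors will be taken in tandem as evidence to suggest GAE treatment efficacy". The model is described with "We will allow a random intercept and slope that is dependent on treatment". The only other result given a conclusion is a non-significant one: "Non-significance of the p-value for this test will be considered inconclusive evidence against the null hypothesis".

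Section 3.2 frames the WOMAC endpoint as "Overall efficacy of treatment as determined by a minimal clinically significant reduction in global" WOMAC score, of 16%, and the VAS endpoint as "Minimal clinically important decrease of 15% on the pain VAS at 1 or 6 months follow-up". Section 7.2 has "Clinical success will be defined as a 16% reduction of the baseline global WOMAC score".

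**The concern.** Section 8.1 gives the probability of one event, a significant test. Section 8.2 names two factors and takes them jointly. At the planning SD, a WOMAC difference of 12.5% of baseline is already significant, so a result can pass the test and still fall short of 16%. The stated power then overstates the chance of meeting the whole criterion.

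The lower-bound argument has the same gap. More visits can sharpen the estimate and help the test. They cannot make an estimate centred on the threshold land above it more than half the time.

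At stake is how the trial's prospects are described. Someone reading 8.1 would expect a treatment with exactly the targeted WOMAC benefit to be declared effective in at least 69% of trials. Under the two-part reading it is about half.

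**Working it through.** **Inputs.** From 3.1: 21 patients at 2:1, so 14 GAE and 7 sham. From 4.2: all expected to complete. From 8.1: means, SDs, percentages, one-sided. From 8.2: alpha 0.05 (8.1 gives none). Assumption: the SD at 6 months equals the baseline SD.

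**Step 1: reproduce the stated powers.** Two-group t-test, df = 14 + 7 − 2 = 19, critical t = 1.729.

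- WOMAC: effect = 0.16 × 12.2 = 1.952; d = 1.952/1.9 = 1.027; SE = 1.9 × √(1/14 + 1/7) = 0.880; noncentrality = 1.952/0.880 = 2.22; power 68.9%. With d rounded to 1.03 it is 69.1%.
- VAS: effect = 0.15 × 72 = 10.8; d = 10.8/13.3 = 0.812; SE = 13.3 × √(1/14 + 1/7) = 6.157; noncentrality = 10.8/6.157 = 1.754; power 51.9%. With d rounded to 0.81 it is 51.7%.

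Both stated figures are therefore single-time-point powers of the significance test, with the effect set as a percentage of the baseline mean.

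**Step 2: smallest significant difference at the planning SD.**

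- WOMAC: 1.729 × 0.880 = 1.52 points; 1.52/12.2 = 12.5%, against a threshold of 16%.
- VAS: 1.729 × 6.157 = 10.65 mm; 10.65/72 = 14.8%, against a threshold of 15%.

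**Step 3: chance of meeting both parts.** This is P(t > 1.729 and estimated difference ≥ 16%/15% of the baseline mean), integrated over the distribution of the pooled variance.

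| | WOMAC | VAS |
|---|---|---|
| Test only, true effect = design effect | 68.9% | 51.9% |
| Both parts, true effect = design effect | 49.8% | 46.5% |
| Significant but below threshold | 19.1% | 5.3% |
| Both parts, true effect = 1.25 × design effect | 70.9% | 63.5% |

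The third row is the whole gap between the first two. With a normal reference for the Wald test, the both-parts row becomes 49.9% and 47.9%.

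**Step 4: can several time points help?** If the true difference equals the threshold and the estimator is unbiased and symmetric, P(estimate ≥ threshold) = 50% whatever the SE. The two-part chance cannot exceed that. For illustration, with the SE cut to 0.6 of its value, test power is 97%/88% but the two-part chance is 50%/50%.

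Under the 8.2 model, taken with an intercept and slope for each arm and complete data at 0, 1, 3 and 6 months, the gain for the test itself is limited. The mean visit time is 2.5 and the sum of squares is 6.25 + 2.25 + 0.25 + 12.25 = 21. The leverage at 6 months is 1/4 + 3.5²/21 = 0.833, so the SE ratio is at least √0.833 = 0.913. At that bound test power is 75.8%/58.2%, and the two-part chance is 50.0% for WOMAC and about 48.6% for VAS.

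**Step 5: sensitivity to crossover.** Sections 3.1, 5.2 and 6.5 let sham patients without improvement at 1 month be unblinded and proceed to embolization. The documents do not say how many to expect. If 5, 4 or 3 sham patients contribute at 6 months (assumed, and treated as random loss), the same t-test gives:

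| Sham patients at 6 months | 7 | 5 | 4 | 3 |
|---|---|---|---|---|
| WOMAC, test only | 69% | 60% | 54% | 46% |
| WOMAC, both parts | 50% | 49% | 47% | 43% |
| VAS, test only | 52% | 44% | 39% | 34% |
| VAS, both parts | 47% | 42% | 38% | 33% |

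**The case against.** The strongest reply is that nothing in 8.1 is miscalculated. It claims power to detect a difference, which is test power, and its figures reproduce. The multiple-visit argument is also sound for the test, since Step 4 shows test power rising. This stands: a reader might infer an arithmetic error in 8.1, and the documents do not support that.

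Second, 8.2 never says that the estimate must reach the threshold. Its wording could mean that the percentage is reported beside the p-value to aid interpretation, and 8.2 also says that each endpoint is evaluated by a single statistical test. A reader might infer that the plan imposes a hard gate; it does not do so explicitly. Still, 8.2 calls the percentage one of two factors taken together as evidence of efficacy, and 3.2 says that efficacy is determined by the minimal reduction. A two-part criterion is the more natural reading.

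Third, 8.2 names no denominator, and 3.2 and 7.2 concern change from baseline rather than a difference between arms. The baseline mean is the natural choice because 8.1 builds its effects on it, but the 6-month sham mean is possible. If that mean fell by an assumed 10% or 20% with the absolute effect unchanged, the two-part chance would be 59% or 65% for WOMAC and 50% or 51% for VAS. If the true effect were instead 16%/15% of the lower sham mean, it would be 49% or 47% and 43% or 38%.

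Fourth, the 50% ceiling is generic to any rule that sets the threshold at the design effect. That is true, and it is why the lower-bound wording cannot be carried over to such a rule.

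Finally, VAS hardly changes, and crossover narrows the gap further. Both points stand. With 5 sham patients contributing, the gap is about 11 points for WOMAC and 2 for VAS. It narrows because test power itself falls, so crossover does not rescue the stated figures.

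**Conclusion.** The point holds as a mismatch between the power statement and the decision criterion. The 69.1% and 51.7% are right as powers of the one-sided test with 14 versus 7 patients. They do not describe the two-part criterion of 8.2 on its natural reading: p < 0.05 together with an estimate of at least 16%/15% of the baseline mean. For that criterion the chance at the design effect is about 50% and 47%, and the claims that power is at least the stated value and will in fact be greater do not hold. The gap is material for WOMAC (about 19 points) and small for VAS (about 5).

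The figures rest on a t-test approximation, an unchanged SD at 6 months, the baseline mean as denominator, and all seven sham patients contributing blinded 6-month data. The 50% ceiling needs only an unbiased, symmetric estimate and a true effect equal to the threshold. If the percentage is descriptive, the stated figures stand as test powers, under the same assumption about the sham arm.

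**What to change.** In 8.1:

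- Label 69.1% and 51.7% as power of the significance test only, and confine the minimum-value and greater-power wording to that test.
- Report about 50% (WOMAC) and 47% (VAS) as the chance of meeting the two-part criterion at the design effect, and about 71% and 64% at 1.25 times it.
- State that these figures are a t-test approximation that assumes all seven sham patients contribute blinded data at 6 months, although crossover is allowed after 1 month.

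In 8.2: if the threshold is required, say so and name the baseline mean as its reference. If the percentage is only descriptive, say that efficacy rests on the p-value alone. The two-part figures are then not needed, and 69.1%/51.7% stand as test powers under the same sham-arm assumption.

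The cost is a few sentences, with no added patients and no change to the model or data collection. If the two-part criterion is kept, the downside is a less favourable stated chance of success, mainly for WOMAC.

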5.2 Method for Assigning Subject to Treatment Groups

Subjects who meet all criteria for study entry and have signed written informed consent will be randomized in a 2:1 allocation of treatment (geniculate artery embolization) versus placebo (angiogram). Patients will be blinded to the study procedure. Each patient will be told at the time of recruitment that they may be

randomly assigned to GAE or sham. If after 1 month if they have not had symptom improvement, their assigned procedure would be revealed only if they had undergone a sham procedure. They will then be allowed to proceed with embolization in Arm C if they elect to proceed. This second procedure should be shorter than a complete angiogram and embolization, as the detailed angiogram will not need to be repeated. See table 1 (study schema). A 2:1 ratio was selected so that patients would be more likely to enroll in the study.

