5.5 Blinding of Study

Following randomization, efforts will be made to blind the subject to the study procedure. Patients will not be informed to their treatment or placebo arm. As the procedures of a diagnostic angiogram and embolization are similar (femoral artery access, angiogram, post-operative care), the subject will inherently not know if he/she received the treatment or placebo. The post-operative staff caring for the patient will not be informed as to the treatment the patient received. Datasets for each arm will be presented for analysis by statistician labeled as treatment arm (i.e. A, B or C).

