6.5 Visit 5a and 5b - 1 Month Follow-Up

Subjects will be seen in clinic or contacted by phone or by teleconference, per the subject's preference, 30 +/- 7 days following GAE or sham procedure. The WOMAC questionnaire and VAS pain score will be completed and subjects will be evaluated for possible adverse events. An MRI of the treated knee will be acquired for those subjects who underwent GAE*. Subjects will also provide an update about the necessity/frequency of pre-established conservative therapies.

For those subjects who do not report improvement in symptoms or worsening, and are in the placebo arm, they will be unblinded and offered to undergo the geniculate artery embolization (Arm C) and then followed at similar follow-up intervals to 12 months (24 hours, 2 weeks, 1 month, 3 months, 6 months, and 12 months).

*MRI is only scheduled at one month in order to evaluate for non-target ischemic injury. These types of injuries will become apparent as early as 24 hours after embolization. Infarcted tissue will still be detectable at one month. Based on our experience with embolization in other areas, it is thought extremely unlikely that new ischemic injury related to the procedure will develop after the one-month follow-up. Additionally, findings that would be detected on later scans may be unrelated to the procedure and confound the data.

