6.8 Visit 7a and 7b - 6 Month Follow-Up for blinded subjects

Subjects will be seen in clinic or contacted by phone or by teleconference, per the subject's preference, 180 +/- 10 days following GAE or sham procedure. The WOMAC questionnaire and VAS pain score will be completed and subjects will be evaluated for possible adverse events. Subjects will also provide an update about the necessity/frequency of pre-established conservative therapies. If an AE is suspected based on change in pain scores or functionality, an appropriate work-up will be performed which may include MRI.

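### Section 8.1 presents 69.1% (WOMAC) and 51.7% (VAS) as minimum power, but both are single-time-point t-test figures with all 7 sham subjects intact and no allowance for the permitted sham crossover

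*Combined protocol and SAP*

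**What the plan says.** Section 8.1 takes a baseline WOMAC mean of 12.2 (SD 1.9) and a baseline VAS mean of 72 (SD 13.3, derived from a range). It reports power for a 16% and a 15% difference against a one-sided alternative and presents each result as a minimum. For WOMAC: "Actual power will be greater than this 69.1% lower bound since our analysis strategy uses data from multiple time points". For VAS: "Actual power will be greater than this 51.7% lower bound since our analysis strategy uses data from multiple time points". It names no test, alpha, per-arm size, dropout or crossover assumption. Section 4.2 expects all 21 subjects to complete.

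The primary analysis in 8.2 is a linear random-coefficient model with a sham-versus-GAE test at one point: "We will compute predicted means, as well as the estimated difference in predicted means, at 6 months for both WOMAC and VAS".

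Sections 3.1, 5.2 and 6.5 provide that a sham subject without improvement at 1 month is unblinded and offered the active procedure. Section 5.2 says: "They will then be allowed to proceed with embolization in Arm C if they elect to proceed". After that the two groups have different schedules. The 6-month visit of the original arms is headed "Visit 7a and 7b - 6 Month Follow-Up for blinded subjects", and Arm C visits are timed from the later GAE (6.11 to 6.13). Section 5.5 has data labelled by arm A, B or C. Section 8.2 mentions a crossover group only for the 12-month medication endpoint, not for the 6-month primary contrast.

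**The concern.** A floor on power has to hold under everything the protocol allows. The only reason 8.1 gives for its floor is that the model uses several visits. It leaves out a loss that the protocol itself permits: sham subjects moving to GAE after 1 month, from a group of 7, before the 6-month contrast. A reader of 8.1 would conclude that true power can only exceed the stated figures. That matters when a non-significant result is interpreted, because 8.2 treats such a result as inconclusive, and how inconclusive it is depends on the real power.

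**Working it through.** **Inputs.** N = 21 at 2:1 (3.1), so 14 GAE and 7 sham. One-sided alternative (8.1), p < 0.05 (8.2). WOMAC difference 0.16 × 12.2 = 1.952, d = 1.952/1.9 = 1.027. VAS difference 0.15 × 72 = 10.8, d = 10.8/13.3 = 0.812.

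**Step 1: reproduce 8.1.** Two-sample t-test, df = 19, critical value 1.729, noncentrality d/√(1/7 + 1/14) = d/0.4629.
- WOMAC: 1.027/0.4629 = 2.219, power 68.9%. With d rounded to 1.03, 69.1%.
- VAS: 0.812/0.4629 = 1.754, power 51.9%. With d rounded to 0.81, 51.7%.

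Other variants miss (WOMAC/VAS): two-sided 0.05 or one-sided 0.025 gives 55.8%/38.4%; a 10:11 split gives 73.3%/55.8%; a normal approximation gives 71.7%/54.4%; one-sample tests with n = 7, 14 or 21 give 77.4-99.8%/60.1-97.4%. The test and the 14/7 split are inferred, but no other variant tried fits both figures.

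**Step 2: give the repeated-measures argument full credit.** The documents state no crossover rate, ICC, slope variance or intercept-slope covariance, so all of these are assumptions. The model is linear in time with visits at 0, 1, 3 and 6 months. Total baseline variance is 1, of which the ICC is the between-patient share. Crossovers contribute baseline and 1-month data only. With Vᵢ the covariance matrix of patient i, SE = √(k′(Σ Xᵢ′Vᵢ⁻¹Xᵢ)⁻¹k), where k picks out the 6-month difference. Power is the chance that a noncentral t (19 df, noncentrality d/SE) exceeds 1.729. Variances are treated as known.

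Section 8.2 makes the intercept and slope dependent on treatment in wording that leaves open whether the arms share a baseline mean, so both readings are shown. No slope variance, ICC 0.3-0.7, WOMAC/VAS:

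| Crossovers of 7 | Arm-specific intercepts | Shared intercept |
|---|---|---|
| 0 | 71-74% / 54-56% | 76-93% / 58-80% |
| 1 | 69-70% / 52-53% | 72-91% / 55-76% |
| 2 | 66-67% / 49-50% | 67-88% / 50-72% |
| 3 | 60-64% / 44-47% | 61-83% / 45-66% |

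Example at ICC 0.5 with 3 crossovers, WOMAC: with arm-specific intercepts SE = 0.512, noncentrality 1.027/0.512 = 2.01, power 61%. With a shared intercept SE = 0.468, noncentrality 1.027/0.468 = 2.19, power 68%.

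**Step 3: the random slope.** Section 8.2 specifies one. With an assumed slope SD of 0.10 baseline SD per month and zero intercept-slope correlation, the between-patient variance plus error at 6 months is 1 + 36 × 0.01 = 1.36. With no crossover, power is then 59-61%/43-45% (arm-specific) or 62-76%/46-59% (shared). With a correlation of -0.5 and arm-specific intercepts it is 72-77%/55-59%. The slope can therefore move power in either direction.

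**The case against.** The best defence is that 8.1 is right about repeated measures. With all sham subjects intact and no growth in variance, the model does beat the single-time-point test on either reading of the intercept. With a shared baseline mean, which randomization would justify, the gain can survive several crossovers: at ICC 0.7 with 3 crossovers, power is 83%/66%, well above 8.1. Even with arm-specific intercepts, one crossover leaves 69-70%/52-53%, about level with the stated figures. This stands. A reader might infer that true power must be below 69.1%/51.7%, or that several visits cannot offset the loss of sham subjects; the documents do not support either.

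Two further inferences also go too far. The first is the much larger loss that would follow if crossovers were kept in the sham group with a full GAE effect. Section 8.2 does not say this would be done, and the separate Arm C and the restriction of the 6-month visit to blinded subjects point away from it. The second is that power is capped near 50% because 8.2 weighs the p-value together with the 16% and 15% differences: "Both these factors will be taken in tandem as evidence to suggest GAE treatment efficacy". That needs a pass/fail reading that 8.2 does not state, and it is a separate question from how 8.1 describes its figures.

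Nor is there an arithmetic error, since both figures reproduce. What the defence cannot supply is the guarantee. A floor that holds only for some unstated values of crossover rate, ICC, slope variance and baseline parameterization is not a floor.

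**Conclusion.** The point holds as a fault of description. The 69.1% and 51.7% are single-time-point t-test power with all 7 sham subjects intact, and 8.1 is wrong to present them as minimums in a design that allows sham crossover before the primary contrast. Actual power could lie on either side. With 3 of 7 crossing over and no slope variance, the illustration runs from 60%/44% to 83%/66%. Slope variance at zero correlation can bring power to 59%/43% with no crossover at all. These ranges rest on the assumed ICC of 0.3-0.7, the assumed slope SD, data kept to 1 month for crossovers, known variances and 19 df. The conclusion that no minimum is guaranteed needs only that some permitted settings fall below the stated figures, and they do under both readings of the intercept.

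**What to change.** In 8.1, describe 69% and 52% as the power of a one-sided 0.05 two-sample t-test at a single time point, 14 against 7, with baseline SDs and every sham subject intact. Delete 'at least' and both sentences that call the figures lower bounds. Add power for the planned model under a stated assumed crossover rate and covariance (ICC, slope variance, intercept-slope covariance, shared or arm-specific baseline mean). That calculation should use the same handling of crossovers' data as the 6-month contrast, so 8.2 needs to state that handling. The cost is wording and possibly a less favourable stated figure; it needs no extra patients.

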4.2 Anticipated Number of Research Subjects

Enrollment into the investigation will be defined as providing informed consent for study participation per IRB policies.

Twenty-one (21) subjects will be enrolled and all are anticipated to complete the study.

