4.3 Inclusion Criteria

- 1. Moderate to severe knee pain (VAS > 50 mm), and
- 2. Pain refractory to at least 3 months* of conservative therapies (antiinflammatory drugs, or physical therapy, or muscle strengthening, or intraarticular injections), and
- 3. Kellgren-Lawrence grade 1, 2 or 3 on radiograph of the knee.
- 4. Age > 40 years.

*3 months was chosen because this time interval is thought adequate for knee pain to be considered refractory to conservative care.

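### Section 8.1's powers of 69.1% and 51.7% are computed correctly but are not lower bounds: they assume that the baseline SD holds at 6 months and that all 21 subjects give 6-month data in their assigned arm

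*Combined protocol and SAP*

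**What the plan says.** Section 8.1 takes its WOMAC inputs from an earlier embolization series: "Using baseline WOMAC means and standard deviations of 12.2 and 1.9, respectively, from the Okuno study". For VAS it starts from a baseline mean of 72 and range of 54 to 100, and uses a range-based method to "derive an estimate of the baseline standard deviation as 13.3". The targets are a "clinically relevant difference of 16% for WOMAC for a one-sided alternative hypothesis" and, for VAS, "power to detect a clinically relevant difference of 15% for VAS for a one-sided alternative hypothesis". Each power is introduced as a minimum and followed by a sentence saying that the true value is higher. For VAS that sentence reads "Actual power will be greater than this 51.7% lower bound since our analysis strategy uses data from multiple time points". No other reason is given.

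Section 8.2 tests the difference between arms in predicted means at 6 months. The model is a line in time with a random intercept and slope, a dependence on treatment, and no further covariates, fitted to data at 0, 1, 3 and 6 months. Efficacy is judged by "considering significance of the p-value (p < 0.05", together with the size of the difference.

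Section 4.3 requires "Moderate to severe knee pain (VAS > 50 mm" at entry. Section 4.2 enrols 21 subjects and says "all are anticipated to complete the study". Section 4.7.2 replaces only subjects who withdraw before GAE. Sections 5.2 and 6.5 let sham subjects without improvement at 1 month be unblinded and offered embolization.

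**The concern.** A lower bound on power must hold however the unknown quantities turn out. These two figures depend on two unknowns that section 8.1 does not mention.

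- **The SD at the time of the test.** The outcome is compared at 6 months, but the SD is a baseline one. For VAS, the source range of 54 to 100 lies wholly above this trial's own entry cut-off of 50 mm, and no cut-off applies at 6 months. The planned model also gives each subject a random slope. That makes the 6-month variance larger than the baseline variance unless intercepts and slopes are sufficiently negatively correlated.
- **The number of subjects with usable 6-month data.** The figures need all 14 v 7. The sham arm is the smaller one, and it is also the arm from which subjects may cross over after 1 month.

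Section 8.2 calls a non-significant result inconclusive. How a reader weighs such a result depends on the real power, and section 8.1 says that power exceeds 51.7% and 69.1%.

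**Working it through.** **Inputs.** One-sided test (8.1); alpha 0.05 (8.2, as 8.1 states none); 21 subjects at 2:1, so 14 v 7 (3.1, 4.2); WOMAC mean 12.2, SD 1.9; VAS mean 72, SD 13.3 (8.1).

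**1. Reproduce the plan's figures.** Power = P(T > t crit), where T is noncentral t with n1 + n2 − 2 degrees of freedom and noncentrality d × √(n1 n2 / (n1 + n2)). For 14 v 7 the root is √(98/21) = 2.160.

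- WOMAC: difference 0.16 × 12.2 = 1.952; d = 1.952/1.9 = 1.027; power 68.9% (stated 69.1%).
- VAS: difference 0.15 × 72 = 10.8 mm; d = 10.8/13.3 = 0.812; power 51.9% (stated 51.7%).

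A two-sided 0.05 test would give 55.8% and 38.4%, which do not fit. The stated figures therefore contain no allowance for a larger follow-up SD or for missing data.

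**2. What several time points can add.** Take visits at 0, 1, 3 and 6 months (mean 2.5, sum of squares about the mean 21) and an intercept and slope for each arm. The 6-month predicted mean then keeps all the between-subject variance and this share of the residual variance:

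1/4 + (6 − 2.5)²/21 = 0.250 + 0.583 = 0.833.

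If r is the residual share of the 6-month variance, the variance falls by the factor 1 − r/6. The saving is at most 16.7%, reached only at r = 1.

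| r | VAS, SD 13.3 | WOMAC, SD 1.9 |
|---|---|---|
| 0 | 52% | 69% |
| 0.5 | 55% | 72% |
| 1 (ceiling) | 58% | 76% |

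**3. SD that cancels the gain.** At the ceiling, 13.3/√0.833 = 14.6 mm and 1.9/√0.833 = 2.08, each about 10% above baseline. At r = 0.5 the factor is 1/√0.917 = 1.044, so about 4% is enough.

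**4. Loss of 6-month data.** Assume 12 v 6 at the stated SDs, with lost subjects contributing nothing. The t-test gives 46% (VAS) and 63% (WOMAC). Adding the model's gain raises these to ceilings of 52.3% and 69.5%, so the stated values are regained only if r exceeds about 0.9. If 4 of 7 sham subjects remain uncrossed (14 v 4, assumed), the t-test gives 39% and 54%.

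**5. Scenarios.** Every SD other than 13.3 and 1.9, and every split other than 14 v 7, is an assumption. Simple t-test:

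| 6-month SD | 14 v 7 | 12 v 6 |
|---|---|---|
| VAS 13.3 | 52% | 46% |
| VAS 15 | 44% | 40% |
| VAS 20 | 30% | 27% |
| VAS 25 | 23% | 21% |
| WOMAC 1.9 | 69% | 63% |
| WOMAC 2.5 | 49% | 44% |
| WOMAC 3.0 | 39% | 35% |

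**The case against.** The best defence is that section 8.1 works from stated inputs, and that its minimum compares a single-time-point test with the repeated-measures model at those inputs. Read that way it is right, as step 2 shows. But the sentence quoted from 8.1 is about actual power, not power conditional on the inputs.

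Second, a reader might infer that true power is much lower than stated. The documents do not support that. They give no 6-month SD, and scores could also compress towards the floor of the scale. Nor can the 86.3% six-month success rate cited in section 1.2 be turned into an SD. It comes from an uncontrolled embolization cohort, its definition of success is not given, and it says nothing about the spread in a sham arm.

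Third, the wording of 8.2 might be read as a common intercept with a treatment-dependent slope, which would borrow strength from baseline. As an ANCOVA approximation with SD × √(1 − ρ²), a VAS SD of 15 mm at ρ = 0.5 acts like 15 × 0.866 = 13.0 mm, slightly better than stated. An SD of 20 mm gives 36% at ρ = 0.5 and 47% at ρ = 0.7, still below 51.7%. Under this reading the point is weaker, but the minimum still fails for larger SDs.

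Fourth, 12 v 6 has no source and ignores partial data. Section 4.7.2 keeps recorded data, 8.2 uses earlier visits, and phone follow-up limits losses. This softens step 4 without restoring a guarantee. The missing-at-random argument in 8.2 concerns validity, not power.

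Finally, the range-restriction argument cannot be extended to WOMAC: 8.1 gives no WOMAC range and 4.3 sets no WOMAC threshold.

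**Conclusion.** The concern holds as a fault in what is claimed, not in the calculation. The figures of 69.1% and 51.7% are correct for a one-sided 0.05 t-test with baseline SDs and full 14 v 7 data. They are not shown to be lower bounds. With arm-specific intercepts and no covariates, the stated reason is worth about 3 percentage points if half the variance is residual, and about 6 to 7 at the ceiling. A 6-month SD about 10% above baseline cancels even the ceiling, and modest loss of 6-month data does so in most cases.

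How far power falls is unknown. The range of 23% to 44% for VAS and 39% to 49% for WOMAC describes assumed SDs (15 to 25 mm; 2.5 to 3.0) with all 21 subjects observed. It is not an estimate of the trial's power.

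**What to change.** In section 8.1:

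- Remove the minimum-power wording and both sentences asserting that actual power is higher.
- State 69.1% and 51.7% as approximate powers for a one-sided 0.05 two-sample test, assuming that the baseline SD applies at 6 months and that all 14 v 7 subjects give 6-month data in their assigned arm.
- Add a short sensitivity table over 6-month SD (VAS 13.3 to 25 mm; WOMAC 1.9 to 3.0) and completers (14 v 7, 12 v 6, and a row for fewer sham subjects remaining uncrossed, such as 14 v 4). Label the SDs and splits as assumptions.

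The cost is a few lines of text and figures that look less favourable. No patients are added, and neither the design nor the analysis changes.
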